5.2 Handling of Study Interventions

All participants will receive an Oculus Quest 2 virtual reality headset for use during the study.

5.4 Adherence Assessment

Patients will be closely monitored by the PI, [name], as well as the treatment and research team. Patients are compensated for their time and contribution to this study, with increased compensation for the 3-month follow-ups. Follow-up will occur at 3-months for both treatment groups.

6. Description of Evaluations

The Schedule of Evaluations will include Recruitment (referral), a Baseline Assessment (informed consent/assent, self-reported questionnaires), Discharge Assessment (self-report questionnaires), and a 3-month follow-up (self-report questionnaires).

6.1 Screening Evaluation

Screening

The study team will recruit adolescent patients and a primary parent from the outpatient rehabilitation department the Department of Rehabilitation at Stanford Children's Health (SCH) at the Pediatric Pain Management Clinic (PPMC). Youth patient and parent will be referred by their clinician at the PPMC. If interested, the parent will tell their clinician that they are interested to allow researchers to contact them.

Consenting Procedure

Before obtaining formal written assent/consent from patients and their parents, clinical providers at the SCH will obtain consent to be approached by members of the research team.

Study staff, which will include a clinical research coordinator (CRC) or postdoctoral fellow trained by [name], will conduct the consent and assent procedure. Eligible participants will be educated about study procedures or any changes in those procedures. Signed consent/assent forms will be kept in a locked secure database in IRB approved REDCap.

6.2 Enrollment, Baseline, and Randomization

Enrollment

Study consenting/assenting and enrollment will take place via Zoom or in person. All procedures will be completed by a clinical research coordinator (CRC) and/or postdoctoral fellows.

Consenting Procedure for Enrollment

This study will follow the *Informed Consent Process for Research* according to the Stanford University Research Compliance Office. Each participant's consenting process will be recorded by the study CRC in the "Screening and Enrollment Log" (MOP Supplemental Materials I) within an online REDCap eCRF. The signed consent/assent documents will be kept in a locked secure database in IRB approved REDCap.

The informed consent process will take place via Zoom or in-person, and participants will have the opportunity to read the consent form and ask any questions they may have at the beginning of the data collection session. Signed consent/assent forms will be stored in a locked secure database. Participants will be reminded that their involvement in this study is completely voluntary, and that they can withdraw at any time without any negative repercussions whatsoever (e.g., with regard to clinical care or healthcare access). They will also be explicitly told that they may leave any question blank for questionnaires or unanswered for the clinical interview if they do not feel comfortable answering. See Supplement Material for the consent and assent form.

Non-English Speaking Participants – Individuals who do not speak or understand English will not be recruited to the study. While we recognize the limitations of this approach, practical considerations necessitate the inclusion of only those who are able to speak or understand English.

Enrollment date will be recorded in the “Screening and Enrollment Log” eCRF, which will also include documentation of inclusion/exclusion criteria.

Baseline Assessment (BAS):

The BAS assessment will consist of self-report measures and a zoom or in-person training session. The child and parent baseline measures will be introduced by a CRC after they conduct the consent/assent process via Zoom or in person.

VR orientation: We will ask youth and caregivers to join a brief zoom call so that trained members of the research team may orientate the family to the VR equipment and help them set it up in the environment in which they will be asked to use the VR by their clinician.

See Supplemental Materials III for baseline self-report measures

Discharge Assessment:

The child and parent will complete discharge measures.

See Supplemental Materials III for discharge assessment measures

Follow-Up Assessments:

The child and parent will complete follow-up measures.

See Supplemental Materials III for follow-up assessment measures

Optional Assessments:

Daily Diary Surveys: Answering questions in the daily diary will take approximately 3 minutes to complete. You will be asked to fill out the daily diary and given the option to answer weekly, daily, and/or when you have PT sessions during study treatment and for one week at 3-month follow-up if you choose. You will be compensated a \$20 bonus as a thank you for your time if you choose to answer these surveys.

Brief Informational Interview: This exploratory study seeks to gather reports from participants after undergoing virtual reality exposure, paying particular attention to the language individuals use to describe their experience. Thus, the study procedure may include an informal and semi-structured interview, that will take place in the clinic after VR exposure. Participants and their parents may be asked to reflect on their condition, and on their experience with the VR module. The interviews may be recorded and transcribed. Personally-identifying information will not be disclosed from these interviews. Audio devices will be kept in a locked office at Stanford University.

Actigraph Watch: Participants can wear a small, electronic study device on your wrist that tracks your activity level and sleep. If they choose to participate in this activity, participants will be asked to wear this from the start of the study until the last study treatment session and responsible for returning this electronic study device at the end of the study treatment period.

See Supplemental Materials III for optional assessment measures

Clinician Measures:

Clinicians will answer brief surveys post VR exposure in session to document use of VR to ensure safety of participants.

See Supplemental Materials III for clinician measures

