7.2 Methods and Timing for Assessing, Recording, and Analyzing Safety Parameters

N/A

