7.3 Adverse Events and Serious Adverse Events

For the purposes of this study, the following AE definitions are used:

Adverse Event (AE): Any unfavorable or unintended sign (including an abnormal laboratory finding), symptom or disease temporally associated treatment interventions, regardless of whether it is considered related to the treatment. AEs are categorized according to the following scale:

Severity Ratings

Adverse Events (AEs) will be rated on the following three-point scale, to the determine the severity of:

- **Mild:** An experience that is transient and requires no special treatment or intervention. The experience does not generally interfere with usual daily activities.
- **Moderate:** An experience that is alleviated with simple therapeutic treatments. This experience impacts usual daily activities. Includes laboratory tests alterations indicating injury, but without long-term risk.
- **Severe:** An experience that requires therapeutic intervention unrelated to clinical trial treatment intervention. The experience interrupts usual daily activities. If hospitalization is required for treatment, this will be classified as an SAE.

Relatedness Ratings

Adverse Events (AEs) will be rated on the following three-point scale, to the degree to which the event appears to be related to the study intervention:

- 0, **Unrelated**
- 1, **Possibly Related**
- 2, **Definitely Related**

Expectedness Ratings

Adverse Events (AEs) will be assessed as to whether they were *expected* to occur or *unexpected*, meaning not anticipated based on current knowledge found in the protocol or based on the treating clinician's experience:

- **Unexpected:** the nature or severity of the event is not consistent with information about the condition under study or intervention in the protocol, consent form, or clinician's experience
- **Expected:** the event is known to be associated with the intervention or condition under study.

Unanticipated Problem (UP): an unanticipated problem involving risk to human participants or others, is one that (1) was unforeseen at the time of its occurrence, (2) is related or possibly related

to participation in the research, and (3) indicates that participants or others are at an increased risk of harm.

Serious Adverse Events (SAE): Any AE that result in any of the following outcomes:

- Death
- Suicide/Homicide Attempt
- Life-Threatening event
- Event requiring inpatient hospitalization

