9. STATISTICAL CONSIDERATIONS

9.1 General Design Issues

To characterize feasibility of a future hybrid effectiveness-dissemination trial of PRVR in routine physiotherapy practice. Hypotheses: PRVR participants will have (1) high patient-reported treatment satisfaction and high clinician-rated patient engagement scores; Clinicians will report high clinical proficiency and self-efficacy in using PRVR.

Analysis Plan: *Satisfaction.* We will examine mean satisfaction scores, clinician rated engagement scores, and clinician proficiency and efficacy with PRVR clinical use.

Adherence/retention. We will examine mean adolescent adherence to survey completion, percent of patients who dropout prior to treatment completion, and VR side effects reported.

Health care costs and pain medication use. We will examine health care and pain medication use by calculating totals via healthcare cost surveys and compared across timepoints.

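### VR side effects are to be reported, but the plan describes no symptom rating by the child before VR, so new and existing symptoms are separated only by judgement afterwards

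*Combined protocol and SAP*

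**What the plan says.** **Endpoint.** Section 9.1, under adherence and retention, lists among the results to be examined "percent of patients who dropout prior to treatment completion, and VR side effects reported". It gives no definition of a side effect and no instrument, reporter, timing or denominator.

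**In-session record.** Section 6.2, Clinician Measures, states: "Clinicians will answer brief surveys post VR exposure in session to document use of VR to ensure safety of participants". The items are deferred: "See Supplemental Materials III for clinician measures".

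**Safety methods.** The section headed "7.2 Methods and Timing for Assessing, Recording, and Analyzing Safety Parameters" is completed only as not applicable, and so is Section 7.1 on safety parameters.

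**Adverse events.** Section 7.3 defines an adverse event to include any unfavourable "symptom or disease temporally associated treatment interventions, regardless of whether it is considered related to the treatment". Each event is then rated unrelated, possibly related or definitely related (0, 1, 2). Section 7.4 adds that parents are asked to notify the team and that staff ask patient and parent at follow-up.

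**Child and parent reports.** Section 6.2 has baseline questionnaires at enrolment ("See Supplemental Materials III for baseline self-report measures"), discharge and follow-up questionnaires, and an optional diary for which participants are "given the option to answer weekly, daily, and/or when you have PT sessions during study treatment". There may also be an "informal and semi-structured interview, that will take place in the clinic after VR exposure".

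**Setting.** The Précis describes a single-arm feasibility study. Section 3 admits 10- to 17-year-olds with localized or diffuse musculoskeletal or neuropathic pain. Section 5.1 has VR used both in session and at home, with treatment running about 6 to 12 weeks.

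**The concern.** A side effect of VR is a change: a symptom that was absent and appears, or was present and gets worse. Measuring a change needs a value from before the exposure or a reliable question about onset. The text describes neither, and a single arm offers no control group to show how often these children would have the same symptoms without VR.

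Two opposite errors are then possible. A symptom the child brought to the session may be counted against VR. Or a real worsening may be set aside because the child is thought always to have it. Which occurs more often would depend on how each clinician handles background symptoms. Many VR side effects are also sensations that the child is best placed to report, whereas the described respondent is the clinician.

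Section 9.1 gives the aim as characterizing the feasibility of a later, larger trial in routine physiotherapy. Side effects are one of the few tolerability results that will inform that step.

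**Working it through.** The plan states no sample size and no side-effect rate, so there is no figure to reproduce. The check is a reading of every place where symptoms could be recorded, followed by an illustration on assumed values.

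**Step 1. Does any described source give a before-and-after comparison for a VR exposure?**

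| Source | Reporter | Timing relative to VR | Per-exposure comparison? |
|---|---|---|---|
| Clinician survey (6.2) | Clinician | After, in session | None described; items not supplied |
| Baseline questionnaires (6.2) | Child, parent | Once, at enrolment | No |
| Discharge and 3-month questionnaires (6.2) | Child, parent | After treatment; at follow-up | No |
| Diary (6.2) | Participant, optional | Frequency chosen by participant; not tied to before or after VR | No |
| Interview (6.2) | Child, parent; may occur | After | No |
| Adverse-event reports (7.4) | Study team, parents; patient and parent asked at follow-up | Any time | No |
| Relatedness rating (7.3) | Rater not stated | After the event | A judgement, not a measurement |

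No row shows a structured rating from immediately before VR. What remains for separating new from existing symptoms is the relatedness judgement, and Section 9.1 does not say whether its count uses that rating.

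**Step 2. What could a post-only count do?** Let *b* be the share of sessions that start with a given symptom and *v* the share of the remaining sessions in which VR newly causes it. Both are assumptions; neither is in the documents.

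*Every symptom present afterwards is counted:* observed = b + (1 − b)v, against true new onset = (1 − b)v.

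| b | v | Observed | True new onset | Ratio |
|---|---|---|---|---|
| 10% | 5% | 10 + 4.5 = 14.5% | 4.5% | 3.2 |
| 10% | 10% | 10 + 9 = 19% | 9% | 2.1 |
| 40% | 5% | 40 + 3 = 43% | 3% | 14.3 |
| 40% | 10% | 40 + 6 = 46% | 6% | 7.7 |

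With v = 0 the observed count is still b.

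*Every symptom present beforehand is discounted:* suppose, as a further assumption, that VR worsens existing symptoms in the same share v of the sessions that start with them. True new-or-worse is then (1 − b)v + bv = v, and the count is (1 − b)v. The fraction missed is b, here 10% to 40%. For example, with b = 40% and v = 10%, 6% is counted against a true 10%.

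**Step 3. What this shows.** The same data can yield an overcount or an undercount depending on a handling rule that the plan does not state. These are the two extreme rules; actual practice may lie between them. The figures show direction only and do not estimate this study's error.

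**The case against.** Several points count on the other side.

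- Section 9.1 does not say that side effects come from the clinician survey. They could be asked of the child in the discharge, follow-up or diary questionnaires. This stands: the link between survey and endpoint is an inference. It also means that the endpoint has no stated source.
- Knowing who answers a survey and when does not show what it asks. An item on whether a symptom began or worsened during VR would meet much of the concern, and a clinician can enter what the child says. This stands, and it cannot be checked because the supplement was not supplied.
- A clinician who treats the child in session may well know how the child felt beforehand. Nothing says otherwise. What is missing is a described record of it.
- The analysis is descriptive, the hypotheses concern satisfaction, engagement and clinician proficiency, and no threshold or go/no-go rule uses the side-effect count. This limits the consequence.

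A reader might go further and infer that side effects cannot be told apart from existing symptoms at all. The documents do not support that, given the relatedness rating, the baseline, the optional diary and the adverse-event routes. A reader might also take the adverse-event definition in Section 7.3 as the counting rule for Section 9.1. It is not stated to be one, and it is followed by relatedness and expectedness ratings.

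**Conclusion.** The concern holds in a limited form. The only in-session survey described is post-exposure and completed by the clinician, no pre-VR rating by the child appears, and safety methods and timing are entered as not applicable. In a single arm of children with chronic pain, separation of new from existing symptoms rests, on the supplied text, on judgement after the fact. The side-effect result may therefore over- or under-count symptoms that VR brings on.

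The size cannot be derived from the documents. It would be wrong to read the 2- to 14-fold range above as a finding: it rests on assumed rates and on counting every existing symptom as a side effect, and its upper end is one corner of the grid. The conclusion also depends on the unseen survey items not already asking about onset. This is a worthwhile, inexpensive improvement to a descriptive result; it does not undermine the study's main aims.

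**What to change.** 1. **Section 6.2, Clinician Measures.** Have the child rate the same few symptom items (0–10, or none/mild/moderate/severe) immediately before and immediately after each in-session VR exposure. The clinician enters both ratings on the existing survey.
2. **Section 9.1.** Define a VR side effect as a symptom that is new, or worse than the pre-VR rating. Report it per session and as the percent of children with at least one.
3. **Scope.** State that this covers in-session use only. No survey tied to home VR use is described, so home events rest on general adverse-event reporting and the optional diary.

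If the supplement already asks about onset or pre-session state, the change may reduce to saying so in Sections 6.2 and 9.1.

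**Cost.** The survey becomes slightly longer, with no extra staff. Asking about symptoms beforehand may prompt some reporting afterwards. That downside is small and should be acknowledged when the result is reported.

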7. SAFETY ASSESSMENTS

As the study is being conducted within a healthcare facility all normal monitoring of safety will be in place. There are few additional safety risks introduced as part of the involvement in the study

procedures. If any risk arises as part of completing study assessments or participating in the treatment, there are physical therapists and medical personnel immediately available to assess the situation and provide assistance. See Appendix B and Appendix C for Adverse and Serious Adverse Event Reporting forms.

7.1 Specification of Safety Parameters

N/A

7.2 Methods and Timing for Assessing, Recording, and Analyzing Safety Parameters

N/A

7.3 Adverse Events and Serious Adverse Events

For the purposes of this study, the following AE definitions are used:

Adverse Event (AE): Any unfavorable or unintended sign (including an abnormal laboratory finding), symptom or disease temporally associated treatment interventions, regardless of whether it is considered related to the treatment. AEs are categorized according to the following scale:

Severity Ratings

Adverse Events (AEs) will be rated on the following three-point scale, to the determine the severity of:

- **Mild:** An experience that is transient and requires no special treatment or intervention. The experience does not generally interfere with usual daily activities.
- **Moderate:** An experience that is alleviated with simple therapeutic treatments. This experience impacts usual daily activities. Includes laboratory tests alterations indicating injury, but without long-term risk.
- **Severe:** An experience that requires therapeutic intervention unrelated to clinical trial treatment intervention. The experience interrupts usual daily activities. If hospitalization is required for treatment, this will be classified as an SAE.

Relatedness Ratings

Adverse Events (AEs) will be rated on the following three-point scale, to the degree to which the event appears to be related to the study intervention:

- 0, **Unrelated**
- 1, **Possibly Related**
- 2, **Definitely Related**

Expectedness Ratings

Adverse Events (AEs) will be assessed as to whether they were *expected* to occur or *unexpected*, meaning not anticipated based on current knowledge found in the protocol or based on the treating clinician's experience:

- **Unexpected:** the nature or severity of the event is not consistent with information about the condition under study or intervention in the protocol, consent form, or clinician's experience
- **Expected:** the event is known to be associated with the intervention or condition under study.

Unanticipated Problem (UP): an unanticipated problem involving risk to human participants or others, is one that (1) was unforeseen at the time of its occurrence, (2) is related or possibly related

to participation in the research, and (3) indicates that participants or others are at an increased risk of harm.

Serious Adverse Events (SAE): Any AE that result in any of the following outcomes:

- Death
- Suicide/Homicide Attempt
- Life-Threatening event
- Event requiring inpatient hospitalization
- Persistent or significant escalation of disability/incapacity

There is no evidence that participation in this treatment trial will increase risk of a serious adverse event (SAE).

7.4 Reporting Procedures

AEs will be identified at any time during participation in this treatment study. Reports of AEs to the Get Living Study team will be assessed and noted. The study team will be informed to notify the PI of any AEs identified during treatment or throughout the duration of enrollment in the study. Parents of patients will also be asked to notify the study team if an AE has occurred. During follow-up contact, the study staff will ask patient and parent if any AEs have occurred since the end of treatment. The known potential risks will be described in informed consent documents and protocol.

All AEs and SAEs will be monitored on a continual basis and documented, by participant, in the respective eCRFs on REDCap. All AEs and SAEs will also be collated across participants into a Master Sheet for presentation to the Safety Monitoring Committee (SMC) at quarterly meetings. In addition, all SAEs and UPs are reported according to the Stanford Medical IRB reporting guidelines (within 10 working days of occurrence). Follow-up remediation will occur within five days of the IRB's response or decision. All AEs will be reviewed quarterly by the PI and SMC.

SAEs and specific treatment intervention-associated AEs will be reported to the PI, [name], and responsible study staff within 24 hours. All SAEs and UPs will be reported to the NIAMS within 48 hours of the investigator becoming aware of the event. There are no SAEs anticipated for this research study.

7.5 Follow-up for Adverse Events

All AE's will be reported to the IRB of record within five days. Follow-up remediation will occur within five days of the IRB's response or decision.

7.6 Safety Monitoring

Oversight of this clinical trial is provided by the Principal Investigator (PI), [name]. The Study Monitoring Committee (SMC) will involve the following individuals:

- [REDACTED] (Medical Expertise) – Institute of Creative Technologies, USC
- [REDACTED] (VR in Pain Expertise) – College of Engineering at U of Washington
- [REDACTED], PT M (Psychology Expertise) – Ottawa Hospital Rehabilitation Centre

This is a multi-site clinical trial involving low risk. The individuals listed above, along with [name] and the Institutional Review Board (IRB), will be responsible for the duties involved with this data monitoring.

Conflict of Interest for Monitoring Bodies. Members of the SMC will have no direct involvement with the PI or the administration of the intervention. Each member will sign a Conflict of Interest (COI) Statement which includes current affiliations, if any, with any steering committees or advisory councils associate with study, pharmaceutical, and biotechnology companies (i.e. stockholder, consultant), and any other relationship that could be perceived as a conflict of interest related to the study and/or associate with commercial or non-commercial interests pertinent to the study objectives.

Protection of Confidentiality. Only de-identified and re-coded data will be presented during open sessions with the SMC. All data, whether in a report or discussed during SMC meetings are kept confidential. Participant identities will be kept confidently unless there are serious safety concerns in which the PI and SMCs involved may request and necessitate the identification of some or all data.

Monitoring Entity Responsibilities. The following are details of members of the study monitoring entity's responsibilities:

- ***Review of Study Documentation:*** The CRC will be responsible for reviewing the Data Safety Monitoring Plan (DSMP), informed consent/assent documents, protocol amendments, and updates to the Manual of Operating Procedures (MOP) and Clinical Protocol for this trial on a weekly basis. The CRC will notify the PI immediately with any PDs and approvals for amendments to the protocol. The PI will have access to all these documents at all times and will be responsible for meeting with the SMC on a quarterly basis.
- ***Subject Accrual:*** Review of subject accrual rates and compliance with inclusion/exclusion criteria will be conducted by the PI and SMC on a quarterly basis to ensure a sufficient number of participants are enrolled, properly screened for eligibility, and targeted goals outlined in the grant proposal are being met.
- ***Enrollment:*** Review of the status of enrolled subjects will be monitored on a regular basis by the CRC and the PI. Quarterly updates will be monitored by the PI and SMC to ensure target enrollment is being met per grant proposal. Monthly enrollment reports will be provided to the NIAMS via NCR by the CRC.
- ***Adherence Data:*** Data on adherence to treatment protocol will be collected on a weekly basis by the CRC and reviewed quarterly by the PI and SMC.
- ***AEs and Rates:*** Adverse Events and the rate of occurrence will be tracked and noted per occurrence and the PI will be notified. Unless indicated necessary, AEs will be reviewed quarterly by the PI and SMC.
- ***SAEs:*** Serious Adverse Events will be monitored in real-time and the PI will be notified within 24 hours of occurrence by the treatment team. The PI, SMC, NIAMS/NCR, and IRB will review this SAE and take appropriate action for the safety of the patient. It will be evaluated at the time of occurrence whether the participant will be withdrawn from the study.
- ***PDs:*** Major PDs will be communicated to the PI immediately. All events will be communicated to the NIAMS via NCR within 48 hours of the PI becoming aware of the event.

